14.2 Subject Compliance Monitoring

Non-adherence to the assigned treatment regimen is defined as missing ≥ 3 treatments in daily sequence, or missing more than 20% of the total number of treatment sessions occurring during the 6 weeks of acute treatment (does not include taper treatments) as outlined in the schedule of events (i.e., 100% compliance = 30 total treatments). However, if the subject does miss a treatment, the subject must not go more than 3 calendar days without a treatment session. Treatments missed during the taper visits are considered protocol deviations. Subjects who are unable to comply with this schedule may be withdrawn from the investigational treatment portion of the study. If a subject receives more than the prescribed number of pulses (i.e. 3000 pulses of good contact), this would be considered an overdose and documented on the SAE form and reported to Neuronetics.

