## **B.** Discussion of Statistical Methods:

This study in adolescent patients is a randomized, parallel-group comparison of treatment with TMS as compared to a sham control. It will be conducted at approximately 16 sites in the United States and Canada, with independent randomization protocols within each site, using a permuted block design to improve balance within site. The primary outcome is the last post-treatment symptom score (LV) measured using the primary efficacy outcome measure (efficacy variable and point of declaration are blinded to the Investigator) for each subject. LV will come from the 6-week visit, unless the data is missing, in which case the last observation will be carried forward (LOCF). The analysis will be performed on the strict intention-to-treat sample of all evaluable subjects, meaning those subjects with a baseline and at least one post-baseline observation available for analysis.

Poorly recruiting sites, defined as those with fewer than 2 randomization blocks, will be pooled into one or more pseudo-sites for purposes of analysis. To ensure that nearly all sites will be of adequate size we will adopt a strict closure policy for sites that do not show early signs of enrollment success. With 16 sites, the average number of subjects per site is approximately 18, so there may be a few sites with fewer than 2 randomization blocks. A site that has not randomized at least 2 subjects in the first quarter of their enrollment may be closed. Then if as many as 2 sites are closed, and one poorly performing site eludes closure, there will be no more than one pseudo-site comprising a total of no more than 2 subjects from the closed site and approximately 11 from the poorly performing site, or no more than 13 subjects in all (i.e. <5% of the total sample).

As noted elsewhere in this protocol, the sites were blinded to the point of primary efficacy declaration in order to improve the study's signal detection ability. Point of declaration for the primary outcome measure is included in this document, which was not shared with any of the study sites.

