#### 3. Per-protocol:

The per-protocol study population (also known as the completer population) is defined as all subjects who signed an informed consent, were enrolled in the study, who met inclusion/exclusion criteria, completed all efficacy assessments at Week 4 or Week 6, and received at least 30 treatments within 6 weeks of treatment initiation of the Phase I acute treatment.

The per-protocol study population 2 is defined as all subjects who signed an informed consent, were enrolled in the study, who met inclusion/exclusion criteria, completed all efficacy assessments at week 4 or week 6, and met the protocol requirements treatment compliance. The protocol defines treatment compliance as a subject cannot miss  $\geq$ 3 treatments in daily sequence or be missing more than 20% of the total number of treatment sessions occurring during the 6 weeks of acute treatment (does not include taper treatments) in either Phase I or Phase II

To satisfy the requirements and definitions of the original study SAP, analyses of the effectiveness outcomes will be performed using per-protocol study population 1, however, the results from per-protocol population 2 will be considered the primary per-protocol analyses for the study given per protocol treatment regimen.

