## **B.** Primary and Secondary Outcomes:

Table 6. Summary of Primary and Secondary Efficacy Study Measures, Prioritized Order of Analysis, and General Definitions of Outcome Measures

Primary Efficacy Outcome Measure	Definitions
HAMD24: total score, intent to treat	HAMD24 total score change from baseline value through
sample using last post-treatment score	week 6
Secondary Efficacy Outcome Measures	Definitions
Continuous outcomes HAMD17, HAMD24 (per protocol), MADRS, CDRS-R, QIDS-A17-R, CGI-S: total score, intent to treat sample using last post-treatment score	For each indicated measure, total score change from baseline value through week 6
Responder categorical outcome HAMD (24 and 17 Item versions) MADRS CDRS-R QIDS-A17-SR CGI-S	For HAMD, MADRS, CDRS-R, and QIDS-A17-SR: proportion of patient population achieving an end of acute phase total score reduction of $\geq$ 50% compared to baseline score
	For CGI-S: End of acute treatment score of 1, 2 or 3.
Factor scores derived from the HAMD including (using the last post-treatment value)	
Anxiety/Somatization	Anxiety/Somatization (sum of items 10, 11, 12, 13, 15, 17)
Core Factor	Core Factor (sum of items 1, 2, 3, 7, 8)
Maier	Maier (sum of items 1, 2, 7, 8, 9, 10)
Gibbons	Gibbons (sum of items 1, 2, 3, 7, 9, 10, 11, 14)
Retardation	Retardation (sum of items 1, 7, 8, 14)
Sleep	Sleep (sum of items 4, 5, 6)
Remitter categorical outcome	
HAMD (24 and 17 Item versions)	For HAMD24: End of acute treatment score < 11
MADDC	For HAMD17: End of acute treatment score < 8
MADRS	For MADRS: End of acute treatment score < 10
CDRS-R	For CDRS-R: End of acute treatment total score < 28
CGI-S	For CGI-S: End of acute treatment score 1 or 2

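### Per-protocol population 2 counts compliance in open-label Phase II, so as written it can remove Phase I non-benefiters from the Phase I per-protocol comparison for events after the endpoint

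*SAP*

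**What the plan says.** SAP Section 3.C.3 defines two per-protocol populations.

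- **Population 1** is tied to Phase I: the subject must have "received at least 30 treatments within 6 weeks of treatment initiation of the Phase I acute treatment".
- **Population 2** replaces that exposure rule with the protocol's compliance rule. A subject may not miss three or more treatments in daily sequence, nor more than 20% of sessions, during "acute treatment (does not include taper treatments) in either Phase I or Phase II".

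The section then states that "per-protocol population 2 will be considered the primary per-protocol analyses for the study".

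The SAP presents the compliance rule as the protocol's own. Protocol Section 14.2 sets the same two thresholds, but for one six-week course ("100% compliance = 30 total treatments"), and it names no phase.

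Four other places matter:

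- SAP Section 2.B takes the primary outcome from the 6-week visit, with LOCF if that visit is missing.
- SAP Section 7.A restricts between-group testing to Phase I and makes Phases II and III descriptive.
- SAP Section 7.B, Table 6, lists the per-protocol HAMD24 result among the secondary continuous outcomes ("HAMD17, HAMD24 (per protocol), MADRS").
- The protocol's Study Summary and SAP Section 1.A offer Phase II only to subjects without protocol-defined benefit in Phase I. The Study Summary estimates 42 such subjects.

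**The concern.** A set used for the Phase I comparison should be fixed by what happened up to the Phase I endpoint. Population 2 also looks at attendance in a later, open-label phase.

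Only Phase I non-benefiters can be in that phase. The extra exclusions therefore fall entirely on patients who did poorly in Phase I, and a patient who benefited can never be removed this way. Membership depends on the outcome being analysed and on behaviour after it was measured. Removing such patients flatters the mean of whichever arm loses more of them.

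At stake are the listed secondary HAMD24 (per protocol) result and the other per-protocol efficacy results. SAP Section 3.C says these are produced to show that the findings are general and consistent.

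**Working it through.** The plan states no figure for this rule, so there is none to reproduce. The check is a comparison of the texts, followed by an illustration of scale.

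**1. Texts side by side**

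| Item | Phase it refers to |
|---|---|
| Protocol 14.2 compliance rule | one 6-week course of 30 treatments, no phase named |
| Per-protocol population 1 | Phase I |
| Per-protocol population 2 | Phase I and Phase II, as a single set |
| Primary outcome (SAP 2.B) | Phase I, week 6 |
| Between-arm testing (SAP 7.A) | Phase I |

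Population 2 alone reaches past the endpoint. The SAP defines no separate Phase II set that would give the Phase II wording another home.

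**2. How many patients**

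Input from the protocol: 42 entrants out of 100 randomised. Assumption: a Phase II breach rate r, for which the documents give no value. Removals = 42 × r.

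- r = 10%: 4.2
- r = 20%: 8.4
- r = 30%: 12.6

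These are upper counts, because an entrant already outside population 2 for Phase I reasons is not an extra removal.

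**3. Shift with equal rates in the two original arms**

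Assumptions: 50 per arm, of whom 28 sham and 14 active subjects enter Phase II; non-benefiters are 10 HAMD24 points worse. If m of 50 enter, the arm mean improves by

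10 × [m/50 − m(1−r)/(50−mr)].

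| r | Sham (m = 28) | Active (m = 14) | Change in difference |
|---|---|---|---|
| 10% | 10 × (0.560 − 25.2/47.2) = 0.26 | 10 × (0.280 − 12.6/48.6) = 0.21 | 0.05 |
| 20% | 10 × (0.560 − 22.4/44.4) = 0.55 | 10 × (0.280 − 11.2/47.2) = 0.43 | 0.13 (unrounded) |
| 30% | 10 × (0.560 − 19.6/41.6) = 0.89 | 10 × (0.280 − 9.8/45.8) = 0.66 | 0.23 |

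Under these assumptions sham gains more, so the difference shrinks.

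**4. Shift with unequal rates**

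The same table, read across rows:

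- 30% active and 10% sham: 0.66 − 0.26 = 0.40 in favour of active.
- 10% active and 30% sham: 0.89 − 0.21 = 0.68 against active.

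A second model uses normal change scores, with the worst 42% overall entering Phase II. The SD comes from the interval that Protocol Section 8.1 gives for the 197-patient adult trial (−4.30 to 0.08): SE = 4.38/(2 × 1.96) = 1.117, and SD = 1.117 × √(197/4) = 7.84.

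With no true effect, the worst 42% average 7.84 × 0.391/0.42 = 7.30 points below the mean (0.391 is the standard normal density at the 42nd percentile). An arm's mean then rises by 7.30 × 0.42r/(1 − 0.42r):

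- r = 30%: 7.30 × 0.126/0.874 = 1.05
- r = 10%: 7.30 × 0.042/0.958 = 0.32
- Difference: 0.73, with its sign set by which arm has the higher rate.

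Simulation of this model with 1,000,000 subjects per arm agrees:

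| True difference | Equal rates, 10-30% | 30% active, 10% sham | 10% active, 30% sham |
|---|---|---|---|
| 0 | about 0 | 0.74 | −0.71 |
| 2.1 | 2.09 to 2.01 | 2.76 | 1.32 |
| 4.0 | 3.96 to 3.83 | 4.59 | 3.18 |

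**The case against.** The best defence is that the sentence means each acute course in turn: Phase I compliance for Phase I analyses, and Phase II compliance for Phase II summaries. The SAP introduces the rule as a restatement of the protocol, whose definition covers one 30-treatment course. Phases I and II have the same acute schedule. SAP Section 4.B also describes subjects entering Phases II and III, which gives the Phase II wording a possible use. This reading may well be the intent. It is stated nowhere, however, and population 2 is written as one set, whereas population 1 is expressly limited to Phase I. If it is the intent, the same sentence needs the same edit.

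The second defence is that little depends on it. SAP Section 4 gives the per-protocol population a supporting role. Population 1 will be analysed alongside it and does not use Phase II attendance, an observed-cases analysis is planned (SAP Section 2.B), and the decision flow in SAP Section 2.D has no per-protocol step. All of this stands. A reader might infer that population 2 is the trial's main robustness check, or that the primary result is exposed; the documents support neither.

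Third, Protocol Section 10.1 keeps the Phase I assignment blinded at Phase II entry, which makes similar breach rates in the two arms plausible, and then the bias is small. That is fair but not assured: one group has already had a full active course without benefit, and the other is starting its first.

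A reader might also take the wording to mean that compliance in one phase is enough, so that a Phase I non-complier stays in. That is strained: a bar on missing sessions in either phase means missing them in neither.

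**Conclusion.** The definition is wrong as written, and the consequence is confined to supporting and secondary analyses. On the plain reading, population 2 conditions a Phase I contrast on the Phase I outcome and on later open-label attendance. Only Phase II entrants who breach compliance there are affected.

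The size rests on assumptions. With 10-30% of 42 entrants breaching, at most about 4-13 of 100 patients are removed. Equal rates by original arm move the HAMD24 difference by about 0.05-0.23 points under the 28/14 split and 10-point gap. Rates of 30% against 10% move it by about 0.7 points in the normal model (0.6 to 0.8 across the true differences tried), and by 0.4 to 0.7 in the simpler one. For scale only, the lower bound on the adolescent effect in SAP Section 2.D is 1.7 points; that criterion does not use this set.

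A reader might infer from the equal-rate case that the bias always runs towards no effect. The documents do not support that. It holds only if breach rates are similar in the two arms, and with unequal rates the shift goes either way. The definitional fault does not depend on which case occurs.

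**What to change.** In SAP Section 3.C.3, state that for all Phase I comparisons population 2 is determined by meeting the Protocol Section 14.2 compliance definition during Phase I acute treatment only. State separately that Phase II compliance is used only for the descriptive Phase II summaries, with its own named set if one is wanted.

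The cost is one sentence in the SAP and one programming flag. No new data are needed, and the primary analysis, population 1 and the success criteria do not change. With the edit, no subject leaves the Phase I per-protocol comparison because of Phase II attendance.

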#### **D.** Center Pooling Methods:

The distribution of patient sample sizes across study sites will be inspected at completion of enrollment. In order to permit a meaningful evaluation of between site variance in the statistical analyses of efficacy outcome, sites with small numbers of patients may be pooled to form a single pseudo-site for purposes of statistical analysis. If a site did not randomize at least one randomization block (6 subjects), they will be combined for 1 pseudo-site.

### E. Handling of Missing Data:

Missing data will be handled using the Last Observation Carried Forward (LOCF).

• Individual Missing items will not be imputed. If one or more items are missing for a given assessment, the total score will be missing for that visit.

44-02219-204, Rev C 21-JAN-2019

Page 12 of 28

- The last non-missing post-baseline assessment will be carried forward if the next scheduled assessment is missing (e.g., if the week 6/ET assessment is missing, the week 4 assessment would be carried forward, if available)
- Baseline observations will not be carried forward (e.g., if a subject is missing the week 4 assessment but has a Week 6 assessment, the subject would not be included in the Week 4 analysis, but would be included in the Week 6 analysis.

A sensitivity analysis may be performed imputing data if deemed necessary.

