10.2 Efficacy and Safety Assessments

Phase I

See Appendix A for schedule of events.

Outcome Assessments

Trained physicians and raters will administer all diagnostic assessments and clinical interviews determining study eligibility during screening and prior to randomization. All study staff will be trained on study procedures by Neuronetics staff.

Outcome screening will occur after both the Informed Assent/Consent Document and the HIPAA Authorization are signed. Baseline assessments will occur prior to the first TMS treatment session. Outcome measures in Phase I will be assessed at the end of treatment weeks 4 and 6. The following outcome assessments will be completed: HAMD/MADRS structured interview, CDRS-R, CGI-S, and QIDS-A17-SR.

Safety Assessments

A physical and complete medical and psychiatric history will be obtained at the screening visit.

Page 26 of 61

Vital signs including height, weight, blood pressure and heart rate will be collected at the baseline visit and at week 6.

Laboratory determination will be measured at screening and include: Blood chemistry, hematology, urine drug screen, and urine pregnancy for female subjects.

Subjects will be evaluated clinically for adverse events at each visit. Serious adverse events (SAEs) will be recorded as they occur and reported to Neuronetics by the study site within one business day of notification.

Cognitive function assessments will be conducted at the baseline visit and at week 6. The following tests from the NIH Toolbox Cognition Battery are used for this study:

- Education
- Handedness
- Attention
 - o Flanker Inhibitory Control and Attention Test
- Episodic Memory
 - Picture Sequence Memory Test
 - Auditory Verbal Learning Test (Rey)
- Executive Function
 - Dimensional Change Card Sort Test
 - Flanker Inhibitory Control and Attention Test
- Language
 - Picture Vocabulary Test
 - Oral Reading Recognition Test
- Processing Speed
 - Pattern Comparison Processing Speed Test
- Memory
 - List Sorting Working Memory Test

The C-SSRS will be completed weekly during TMS treatment to assess worsening of illness and suicidality. The YMRS will be completed at baseline and will be repeated based on reported change in symptoms.

Air conduction thresholds will be assessed for both left and right ears at the baseline visit and at week 6.

Phase II

See Appendix B for schedule of events. The schedule of efficacy and safety measures for Phase II will be identical to that of Phase I.

Phase III

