The null hypothesis will be tested in an analysis of covariance of the LV (value from 6-week visit unless it is missing, then LOCF used), using baseline score, and ATR medication resistance level as fixed effect covariates, adjusting for site differences using a random effect. As discussed elsewhere, the ATR medication resistance levels will group subjects categorically by number of medications which have shown an adequate degree of resistance for that subject. These resistance levels will be grouped into two categories in statistical model, 0-1 in the current episode or 2-4 in the current episode, unless the final distribution of ATR scores in the study population suggests another allocation would be more statistically appropriate. All tests are two-sided, at the 5% level. The primary outcome should be available and meaningful for nearly all subjects, so the main analysis will be by strict intention-to-treat as defined above. An analysis of observed cases only will be performed as a secondary outcome measure. A site by treatment interaction analysis will be done as a secondary analysis to see if there is significant heterogeneity in the effect of TMS across sites. In particular, we will examine site-specific treatment effects (with confidence intervals) to test for evidence of true reversal of effect.

Secondary outcomes include other continuous measures, and within-subject dichotomous variables as outlined in the efficacy variables described elsewhere in this protocol. The treatment effect null hypothesis will be tested by logistic regression on treatment group assignment with adjustment for site and ATR medication resistance level. In addition, the longitudinal symptom scores will be analyzed with a general linear model adjusting for baseline scores and ATR medication resistance level, using a saturated means model for time since baseline, with treatment effect parameterized by a linear effect in time. The correlation of scores within individuals over time will be handled by allowing a within-subjects residual covariance matrix selected by exploration of the sample semi-variogram, as described by Diggle, Liang and Zeger. If this exploration reveals that a mixed model approach will fit the covariance structure better, random effects will be included in the model. As in the main analysis, site by treatment interactions will be tested.

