## Attachments

Attachment I. Scoring Algorithms and Conventions for Major Symptom Assessme	ents:
---	-------

Assessment Tool	Scoring Methods/Conventions
Hamilton Depression Rating	Total Score –
Scale, 24 and 17 Item versions	17 Item Version: Sum of items 1 through 17
(HAMD24, HAMD17)	24 Item Version: Sum of items 1 through 24
	Response –
	Criterion for both versions: $\geq$ 50% reduction compared to baseline
	(Visit 2) total score
	Remission –
	Criterion for HAMD17: Total score < 8
	Criterion for HAMD24: Total score < 11
	Factor Scores –
	Anxiety/Somatization: Total of items 10, 11, 12, 13, 15, 17
	Core Depression: Total of items 1, 2, 3, 7, 8
	Maier: Total of items 1, 2, 7, 8, 9, 10
	Gibbons: Total of items 1, 2, 3, 7, 9, 10, 11, 14
	Retardation: Total of items 1, 7, 8, 14
	Sleep: Total of items 4, 5, 6
Montgomery-Asberg	Total Score –
Depression Rating Scale	Sum of items 1 through 10
(MADRS)	Response Criterion: $\geq$ 50% reduction compared to baseline
	Remission Criterion: Total score < 10
CDRS-R	Total Score –
	Child Rating Scale score: Sum of Items 1 through 17
	Response Criterion: $\geq$ 50% reduction compared to baseline
	Remission Criterion: Total score < 28
Clinician Global Impressions	Integer score on 7 point scale
– Severity (CGI-S)	Item Score and Categorical Distribution reported
	Response Criterion: Score of 3 or less
	Remission Criterion: Score of 2 or less
QIDS-A17-SR	Total Score –
	Sum of the following:
	1) Highest score of any sleep item (Items 1 thru 4)
	2) Highest score of either the mood sad or mood irritable item
	(Items 5 or 6) $(1 + 1)$
	3) Highest score on any 1 appetite/weight item (Items 7 thru 10)
	4) Items 11, 12, 13, 14, 15 each scored as reported
	5) Highest score on either of the 2 psychomotor items (Items 16 or 17)
	Response Criterion: $\geq$ 50% reduction compared to baseline
	$\overline{\text{Remission}}$ Criterion: Total score < 6

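### One missing item voids a whole scale total, so near-complete Week 6 HAMD24 scores give way to Week 4 scores and some QIDS-A17-SR totals that are fully known are discarded

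*SAP*

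**What the plan says.** SAP Section 3.E rules out item-level repair: "Individual Missing items will not be imputed". It continues: "If one or more items are missing for a given assessment, the total score will be missing for that visit". At visit level the same section adds that "if the week 6/ET assessment is missing, the week 4 assessment would be carried forward, if available", and it does not allow baseline to be carried forward.

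SAP Section 2.B defines the analysed value in the same way: "LV (value from 6-week visit unless it is missing, then LOCF used". Protocol Section 10.2 leaves only one earlier on-treatment score to fall back on: "Outcome measures in Phase I will be assessed at the end of treatment weeks 4 and 6".

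SAP Attachment I gives the scoring. HAMD24 sums 24 items, and HAMD17 sums the first 17 of them. QIDS-A17-SR adds items 11-15 to the highest item in each of four groups: sleep ("Highest score of any sleep item (Items 1 thru 4"), mood (items 5-6), appetite/weight ("Highest score on any 1 appetite/weight item (Items 7 thru 10") and psychomotor (items 16-17). Attachment I has no missing-item rule of its own, so Section 3.E governs every scale.

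**The concern.** **Primary endpoint.** A Week 6 interview that lacks one rating out of 24 counts as no interview. The Week 4 total then stands in for it, although 23 ratings from the right visit are in hand. Scores are still expected to move between those visits. In the open-label pilot cited in SAP Section 2.A, mean CDRS-R went from 40.1 at treatment 20 to 32.6 at treatment 30 (a different scale, without a control arm). If Week 4 is also incomplete, the subject has no HAMD24 value and may fall outside the evaluable set, which SAP Section 3.C defines by a complete post-baseline observation.

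**QIDS-A17-SR.** This is the efficacy scale labelled as self-report, completed from age 12. Where a group counts only its highest item and one answered item is already at the top score, a blank elsewhere in that group cannot change the total. Voiding it gains nothing.

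**HAMD17 and factor scores.** These are subsets of the HAMD24 items. The text does not say whether a blank among items 18-24 also voids them, so two programmers could derive different data sets.

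At stake is some avoidable noise in the primary analysis and avoidable missingness in a secondary scale.

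**Working it through.** The plan states no item-missing rate, so it has no figure to reproduce. All rates below are assumptions, with blanks taken as independent across items.

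**1. HAMD24 totals voided.** With blank rate q per item, the chance of at least one blank in 24 is 1 - (1 - q)^24.

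| q | voided |
|---|---|
| 0.1% | 2.4% |
| 0.2% | 4.7% |
| 0.5% | 11.3% |
| 1% | 21.4% |

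If visits are also independent, the chance that Weeks 4 and 6 are both incomplete is 0.047^2 = 0.2% at q = 0.2% and 0.113^2 = 1.3% at q = 0.5%.

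**2. Error for an affected subject.** Assume a Week 4 to Week 6 change with mean 1.5-3 points and SD 4-6. The root-mean-square error from using Week 4 is sqrt(mean^2 + SD^2):
- sqrt(1.5^2 + 4^2) = 4.3
- sqrt(3^2 + 6^2) = 6.7

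Prorating multiplies the 23-item sum by 24/23. Sums of 10, 15, 20 and 25 become 10.43, 15.65, 20.87 and 26.09, so 0.43-1.09 points are added. In simulation, prorating one item had a root-mean-square error of 0.69-0.87. That figure depends on assumed item ranges and correlations, which the documents do not give.

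**3. Effect on an arm mean.** Voided share times mean change:
- 0.047 x 1.5 = 0.07 points
- 0.113 x 3 = 0.34 points

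The treatment difference moves by this much only if all the Week 4 to Week 6 change happens in one arm. With equal change in both arms the shift cancels.

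**4. QIDS-A17-SR totals voided.** 1 - (1 - q)^17 gives 8.2% at q = 0.5% and 15.7% at q = 1%.

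**5. Share of those that are exactly known.** Assume items scored 0-3 and one blank, equally likely to be any of the 17 items. Eight items lie in the two four-item groups, four in the two two-item groups, and five (items 11-15) always count. With m the chance that an answered item is at the maximum, the share is (8/17)[1 - (1 - m)^3] + (4/17)m.
- Uniform scores, m = 0.25: (8/17)(0.578) + (4/17)(0.25) = 33%.
- Milder scores (40/30/20/10% for 0/1/2/3), m = 0.10: (8/17)(0.271) + (4/17)(0.10) = 15%.

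Allowing more than one blank per form lowers these slightly, to about 31-32% and 14-15% in simulation.

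**6. A looser count, for contrast.** Totals with no usable answer for some component number 1 - (1 - q)^5 (1 - q^4)^2 (1 - q^2)^2, or 2.5% at q = 0.5% and 4.9% at q = 1%. Against step 4, about 69% of voided totals have at least one answer in every group. In many of these the highest answered item is only a lower bound for its group, so 69% is not the share that is known.

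**The case against.** **The rule is clear and set in advance, and blanks may be rare.** This stands. HAMD and MADRS are collected by structured interview with trained raters (Protocol Section 10.2), and Protocol Section 17.3 describes edit checks and queries. However, nothing makes every item mandatory, data may be captured on paper and entered later, and a late query cannot properly recover an adolescent's unanswered item. A skipped page would exceed any small-item threshold and would not be rescued.

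**Other analyses test the carrying forward.** This also stands in part. SAP Section 2.B commits to an observed-cases analysis and a longitudinal model. They would help show whether carried-forward scores drive the result, but they do not bring back the 23 ratings. The imputation sensitivity analysis in Section 3.E is optional, with no method or trigger.

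**Stronger readings a reader might infer, which the documents do not support:**
- *The SAP contradicts itself.* It does not. Attachment I says how totals are formed, and Section 3.E says what happens when an item is missing.
- *About two thirds of voided QIDS totals are usable as they stand.* That is the looser count in step 6, which needs an imputation.
- *Every correctly completed QIDS form would be void because only one appetite direction is answered.* The form is not in the documents, and an item skipped by design need not count as missing.
- *Subjects are routinely lost through an incomplete baseline.* Baseline HAMD24 is an entry test (Protocol Section 11.1), randomization waits for pre-study procedures to be completed (Section 12.3), and Appendix A requires baseline assessments to be complete before the first treatment.
- *An error of 4.3-6.7 points swamps the 1.7-point success floor.* The first is an error in one subject's score and the second a difference between arm means. The comparable figure is 0.07-0.34.

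**Prorating must suit the pooled analysis.** HAMD24 is combined with two adult trials, so scoring should match across studies where item data exist. The fix provides for this.

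**Conclusion.** The point holds as avoidable information loss. As written, SAP Section 3.E replaces a Week 6 HAMD24 with one unrated item by the Week 4 total, and voids QIDS-A17-SR totals that the blank item cannot alter. For an affected subject, prorating one item loses much less than substituting a score two weeks older.

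The effect on the trial is probably small. The shift in an arm mean is about 0.07-0.34 points, resting on assumed blank rates of 0.2-0.5% per item and an assumed mean change of 1.5-3 points, and it largely cancels if the arms change alike. About 15-33% of voided QIDS totals are exactly known, assuming 0-3 items, a single blank, and uniform or milder scores. None of these inputs is in the documents. The change is worth making because it is cheap; the primary conclusion does not hang on it. Severity: COULD.

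**What to change.** Before unblinding, amend SAP Section 3.E as follows.

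- **QIDS-A17-SR.** Keep the total whenever the blank item cannot change it, that is, when it lies in a highest-of group with an answered item at the maximum. If the highest answered item is used in other cases, label it an imputation that can only lower the total, and flag those records.
- **HAMD24, HAMD17, MADRS, CDRS-R.** If no more than 10% of items are missing, prorate from the rated items. Otherwise set the total to missing and apply the visit-level rule. With 24, 17, 10 and 17 items, this allows 2, 1, 1 and 1 missing items. The 10% limit is a judgement, not a figure from the documents, and should be fixed in advance.
- **HAMD17 and factor scores.** Void them only for blanks among their own items.
- **Meta-analysis.** Apply the same HAMD24 rule to the adult trials where item data exist, and say so where they do not.
- **Reporting.** Count affected subjects by arm and visit, and repeat the primary analysis under the present all-items rule as a sensitivity analysis.

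The cost is a few sentences of SAP text and a few lines of derivation code. The downside is a small single-item imputation in a few subjects, which the flags and the sensitivity analysis make visible.
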